7.2.2 Reporting of Pregnancy and Lactation to the Sponsor and to Merck

Although pregnancy and lactation are not considered AEs, it is the responsibility of investigators or their designees to report any pregnancy or lactation in a subject (spontaneously reported to them) that occurs during the trial.

Pregnancies and lactations that occur after informed consent form signing must be reported by the investigator if they cause the subject to be excluded from the trial or are the result of a protocol-specified intervention, including but not limited to washout or discontinuation of usual therapy, diet, placebo treatment, or a procedure.

Pregnancies and lactations that occur from the time of informed consent signing through 120 days following cessation of treatment or 30 days following cessation of treatment if the subject initiates new anticancer therapy, whichever is earlier, must be reported by the investigator. All reported pregnancies must be followed to the completion/termination of the pregnancy. Pregnancy outcomes of spontaneous abortion, missed abortion, benign hydatidiform mole, blighted ovum, fetal death, intrauterine death, miscarriage, and stillbirth must be reported as serious events (Important Medical Events). If the pregnancy continues to term, the outcome (health of infant) must also be reported.

Such events must be reported within 24 hours to the Sponsor ([contact]; [contact]) and within 2 working days to Merck Global Safety (Attn: Worldwide Product Safety; [contact]).

7.2.3 Immediate Reporting of Adverse Events to the Sponsor and to Merck

7.2.3.1 Serious Adverse Events

A SAE is any untoward medical occurrence that at any dose:

- Results in death;
- Is life threatening;
- Results in persistent or significant disability/incapacity;
- Results in or prolongs an existing inpatient hospitalization, unless hospitalization is for:
 - routine treatment or monitoring of the studied indication and not associated with any deterioration in condition

- elective or preplanned treatment for a preexisting condition that is unrelated to the indication under study and has not worsened since the start of study drug
- treatment on an emergency outpatient basis for an event not fulfilling any of the definitions of a SAE given above and not resulting in hospital admission
- social reasons and respite care in the absence of any deterioration in the subject's general condition;
- Is a congenital anomaly/birth defect;
- Is another important medical event. This refers to an AE that may not result in death, be immediately life threatening, or require hospitalization, but may be considered serious when, based on appropriate medical judgment, may jeopardize the patient, require medical or surgical intervention to prevent one of the outcomes listed above, or involves suspected transmission via a medicinal product of an infectious agent.
- **Note:** In addition to the above criteria, AEs meeting either of the below criteria, although not serious per International Conference on Harmonisation (ICH) definition, are reportable to the Merck in the same timeframe as SAEs to meet certain local requirements. Therefore, these events are considered serious by Merck for collection purposes.
 - Is a new cancer (that is not a condition of the study);
 - Is associated with an overdose.

Refer to Table 6 for additional details regarding each of the above criteria.

From the time of informed consent form signing, any SAE or follow up to a SAE, including death due to any cause other than progression of the cancer under study (reference Section 7.2.3.1 for additional details), that occurs to any subject must be reported within 24 hours to the Sponsor ([contact]; [contact]) and within 2 working days to Merck Global Safety if it causes the subject to be excluded from the trial or is the result of a protocol-specified intervention, including but not limited to washout or discontinuation of usual therapy, diet, placebo treatment, or a procedure.

From the time of informed consent form signing through 90 days following cessation of treatment or 30 days following cessation of treatment if the subject initiates new anticancer therapy, whichever is earlier, any SAE or follow up to a SAE, including death due to any cause other than progression of the cancer under study (reference Section 7.2.3.1 for additional details), whether or not related to the study treatment, must be reported within 24 hours to the Sponsor and within 2 working days to Merck Global Safety.

Additionally, any SAE considered by an investigator who is a qualified physician to be related to the study treatment that is brought to the attention of the investigator at any time following consent through the end of the specified safety follow-up period specified in the paragraph above or at any time outside of the time period specified in the previous paragraph also must be reported immediately to the Sponsor and to Merck Global Safety.

All subjects with SAEs must be followed up for outcome.

SAE reports and any other relevant safety information are to be forwarded to the Merck Global Safety [contact]

A copy of all 15 Day Reports and Annual Progress Reports is submitted as required by the FDA, European Union, Pharmaceutical and Medical Devices agency, and other local regulators. Investigators will cross reference this submission according to local regulations to the Merck Investigational Compound Number (IND, CSA, etc.) at the time of submission. Additionally investigators will submit a copy of these reports to Merck & Co., Inc. (Attn: Worldwide Product Safety; [contact]) at the time of submission to the FDA.

7.2.3.2 Events of Clinical Interest

Selected non-serious and serious AEs are also known as ECI and must be reported within 24 hours to the Sponsor ([contact]; [contact]) and within 2 working days to Merck Global Safety (Attn: Worldwide Product Safety; [contact]).

From the time of informed consent form signing, any ECI or follow up to an ECI that occurs to any subject must be reported within 24 hours to the Sponsor and within 2 working days to Merck Global Safety if it causes the subject to be excluded from the trial or is the result of a protocol-specified intervention, including but not limited to washout or discontinuation of usual therapy, diet, placebo treatment, or a procedure.

From the time of informed consent form signing through 90 days following cessation of treatment or 30 days following cessation of treatment if the subject initiates new anticancer therapy, whichever is earlier, any ECI or follow up to an ECI, whether or not related to the study treatment, must be reported within 24 hours to the Sponsor and within 24 hours to Merck Global Safety.

ECIs for this trial include:

1. an overdose of pembrolizumab, as defined in Section 7.2.1 - Definition of an Overdose for This Protocol and Reporting of Overdose to the Sponsor, that is not associated with clinical symptoms or abnormal laboratory results.
2. an elevated AST or ALT lab value that is greater than or equal to 3 X ULN and an elevated total bilirubin lab value that is greater than or equal to 2 X ULN and, at the same time, an alkaline phosphatase lab value that is less than 2 X ULN, as determined by way of protocol-specified laboratory testing or unscheduled laboratory testing.*

*Note: These criteria are based upon available regulatory guidance documents. The purpose of the criteria is to specify a threshold of abnormal hepatic tests that may require an additional evaluation for an underlying etiology.

7.2.3.3 Protocol-Specific Exceptions to Serious Adverse Event Reporting

Efficacy endpoints as outlined in this section will not be reported to Merck as described in Section 7.2.3- Immediate Reporting of Adverse Events to the Sponsor and to Merck, unless there is evidence suggesting a causal relationship between the study treatment and the event. Any such event will be submitted to the Sponsor within 24 hours and to Merck Global Safety within 2 working days either by electronic or paper media.

Specifically, the suspected/actual events covered in this exception include any event that is disease progression of the cancer under study.

The Sponsor will monitor unblinded aggregated efficacy endpoint events and safety data to ensure the safety of the subjects in the trial. Any suspected endpoint which upon review is not progression of the cancer under study will be forwarded to Merck Global Safety as a SAE within 2 working days of determination that the event is not progression of the cancer under study.

Hospitalization related to convenience (e.g., transportation issues, etc.) will not be considered a SAE.

7.2.4 Evaluating Adverse Events

An investigator who is a qualified physician will evaluate all AEs according to the NCI CTCAE v4.03. Any AE which changes CTCAE grade over the course of a given episode will have each change of grade recorded on the Adverse Event CRFs/worksheets.

All AEs regardless of CTCAE grade must also be evaluated for seriousness.

Table 6 Evaluating Adverse Events

An investigator who is a qualified physician will evaluate all AEs as to:

V4.03 CTCAE Grading	Grade 1	Mild; asymptomatic or mild symptoms; clinical or diagnostic observations only; intervention not indicated.
	Grade 2	Moderate; minimal, local, or noninvasive intervention indicated; limiting age-appropriate instrumental activities of daily living (ADL).
	Grade 3	Severe or medically significant but not immediately life-threatening; hospitalization or prolongation or hospitalization indicated; disabling; limiting self-care ADL.
	Grade 4	Life-threatening consequences; urgent intervention indicated.
	Grade 5	Death related to AE
Seriousness	A SAE is any untoward medical occurrence that at any dose:	
	† Results in death ; or	
	† Is life threatening ; or places the subject, in the view of the investigator, at immediate risk of death from the event as it occurred (Note: This does not include an AE that, had it occurred in a more severe form, might have caused death.); or	
	† Results in a persistent or significant disability/incapacity (substantial disruption of one's ability to conduct normal life functions); or	
	† Results in or prolongs an existing inpatient hospitalization (hospitalization is defined as an inpatient admission, regardless of length of stay, even if the hospitalization is a precautionary measure for continued observation. (Note: Hospitalization for an elective procedure to treat a pre-existing condition that has not worsened is not a SAE. A pre-existing condition is a clinical condition that is diagnosed prior to the use of the study treatment and is documented in the subject's medical history.); or	
	† Is a congenital anomaly/birth defect (in offspring of subject taking the product regardless of time to diagnosis); or	
	Is a new cancer (that is not a condition of the study) (although not serious per ICH definition, is reportable to the Sponsor within 24 hours and to Merck within 2 working days to meet certain local requirements); or	
Is an overdose (whether accidental or intentional). Any AE associated with an overdose is considered a SAE for collection purposes. An overdose that is not associated with an AE is considered a non-serious ECI and must be reported within 24 hours to the Sponsor and to Merck within 2 working days.		

	Other important medical events that may not result in death, not be life threatening, or not require hospitalization may be considered a SAE when, based upon appropriate medical judgment, the event may jeopardize the subject and may require medical or surgical intervention to prevent one of the outcomes listed previously (designated above by a †).	
Duration	Record the start and stop dates of the AE. If less than 1 day, indicate the appropriate length of time and units	
Action taken	Did the AE cause the study treatment to be discontinued?	
Relationship to the study treatment	Did the study treatment cause the AE? The determination of the likelihood that the study treatment caused the AE will be provided by an investigator who is a qualified physician. The investigator's signed/dated initials on the source document or worksheet that supports the causality noted on the AE form, ensures that a medically qualified assessment of causality was done. This initialed document must be retained for the required regulatory time frame. The criteria below are intended as reference guidelines to assist the investigator in assessing the likelihood of a relationship between the study treatment and the AE based upon the available information. The following components are to be used to assess the relationship between the study treatment and the AE; the greater the correlation with the components and their respective elements (in number and/or intensity), the more likely the study treatment caused the AE:	
	Exposure	Is there evidence that the subject was actually exposed to the study treatment such as: reliable history, acceptable compliance assessment, expected pharmacologic effect, or measurement of drug/metabolite in bodily specimen?
	Time Course	Did the AE follow in a reasonable temporal sequence from administration of the study treatment? Is the time of onset of the AE compatible with a drug-induced effect?
	Likely Cause	Is the AE not reasonably explained by another etiology such as underlying disease, other drug(s)/vaccine(s), or other host or environmental factors

Relationship to Merck Product (continued)	The following components are to be used to assess the relationship between Merck product and the AE: (continued)	
	Dechallenge	
Was the Merck product discontinued or dose/exposure/frequency reduced?
 
If yes, did the AE resolve or improve?
 
If yes, this is a positive dechallenge. If no, this is a negative dechallenge.
 
(Note: This criterion is not applicable if: (1) the AE resulted in death or permanent disability; (2) the AE resolved/improved despite continuation of the Sponsor's product; or (3) the trial is a single-dose drug trial); or (4) Sponsor's product(s) is/are only used one time.)

	Rechallenge	
Was the subject re-exposed to the Merck product in this study?
 
If yes, did the AE recur or worsen?
 
If yes, this is a positive rechallenge. If no, this is a negative rechallenge.
 
(Note: This criterion is not applicable if: (1) the initial AE resulted in death or permanent disability, or (2) the trial is a single-dose drug trial); or (3) Sponsor's product(s) is/are used only one time).
 
NOTE: IF A RECHALLENGE IS PLANNED FOR AN AE WHICH WAS SERIOUS AND WHICH MAY HAVE BEEN CAUSED BY THE MERCK PRODUCT, OR IF REEXPOSURE TO THE MERCK PRODUCT POSES ADDITIONAL POTENTIAL SIGNIFICANT RISK TO THE SUBJECT, THEN THE RECHALLENGE MUST BE APPROVED IN ADVANCE BY THE SPONSOR AS PER DOSE MODIFICATION GUIDELINES IN THE PROTOCOL.

	Consistency with Trial Treatment Profile	
Is the clinical/pathological presentation of the AE consistent with previous knowledge regarding the Merck product or drug class pharmacology or toxicology?

The assessment of relationship will be reported on the CRFs/worksheets by an investigator who is a qualified physician according to his/her best clinical judgment, including consideration of the above elements.
		
Record one of the following	Use the following scale of criteria as guidance (not all criteria must be present to be indicative of Merck product relationship).	
Yes, there is a reasonable possibility of Merck product relationship.	
There is evidence of exposure to the Merck product. The temporal sequence of the AE onset relative to the administration of the Merck product is reasonable. The AE is more likely explained by the Merck product than by another cause.
	
No, there is not a reasonable possibility of Merck product relationship	
Subject did not receive the Merck product OR temporal sequence of the AE onset relative to administration of the Merck product is not reasonable OR the AE is more likely explained by another cause than the Merck product. (Also entered for a subject with overdose without an associated AE.)
	

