3.2 Secondary Objectives

Objectives:

(1) To determine the duration of response (DoR) of ADV/HSV-tk + valacyclovir therapy in combination with SBRT used as a window of opportunity treatment before pembrolizumab in patients with metastatic TNBC and metastatic NSCLC.

- (2) To determine the overall survival (OS) rate of ADV/HSV-tk + valacyclovir therapy in combination with SBRT used as a window of opportunity treatment before pembrolizumab in patients with metastatic TNBC and metastatic NSCLC.
- (3) To determine the progression-free survival (PFS) rate of ADV/HSV-tk + valacyclovir therapy in combination with SBRT used as a window of opportunity treatment before pembrolizumab in patients with metastatic TNBC and metastatic NSCLC.
- (4) To document the toxicities associated with ADV/HSV-tk + valacyclovir therapy in combination with SBRT used as a window of opportunity treatment before pembrolizumab in patients with metastatic TNBC and metastatic NSCLC. Toxicity will be defined as any treatment-related death or any \geq Grade 3 hematological toxicity excluding alopecia and constitutional symptoms, as assessed by the National Cancer Institute Common Terminology Criteria for Adverse Events (NCI CTCAE) v4.03.
- (5) To document the antitumor activity of ADV/HSV-tk + valacyclovir therapy in combination with SBRT used as a window of opportunity treatment before pembrolizumab in patients with metastatic TNBC and metastatic NSCLC, as assessed by the RECIST 1.1. Modified irRC will also be documented.
- (6) To estimate the clinical benefit rate (CBR) of ADV/HSV-tk + valacyclovir therapy in combination with SBRT used as a window of opportunity treatment before pembrolizumab in patients with metastatic TNBC and metastatic NSCLC.

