The occurrence of AEs should be sought by non-directive questioning of the patient at each study visit. AEs may also be detected when they are volunteered by the patient during or between visits or through physical examination, laboratory test, or other assessments. As far as possible, each AE should be evaluated to determine:

1. Severity grade (CTCAE Grade 1–4)
2. Duration (Start and end dates or if continuing at the Safety Follow-up Visit)
3. Relationship to the study treatment (Reasonable possibility that AE is related: No, Yes)
4. Action taken with respect to study or investigational treatment (none, dose adjusted, temporarily interrupted, permanently discontinued, hospitalized, unknown, not applicable)
5. Whether medication or therapy was given (no concomitant medication/non-drug therapy, concomitant medication/non-drug therapy)
6. Outcome (not recovered/not resolved, recovered/resolved, recovering/resolving, recovered/resolved with sequelae, fatal, unknown)
7. Whether it is serious, where a SAE is defined as in Section 7.2.3.1.

All AEs should be treated appropriately. Such treatment may include changes in study treatment including possible interruption or discontinuation, starting or stopping concomitant treatments, changes in the frequency or nature of assessments, hospitalization, or any other medically required intervention. Once an AE is detected, it should be followed until its resolution, and assessment should be made at each visit (or more frequently, if necessary) of any changes in severity, the suspected relationship to the study drug, the interventions required to treat it, and the outcome.

7.2.1 Definition of an Overdose for This Protocol and Reporting of Overdose to the Sponsor and to Merck

For purposes of this trial, an overdose of pembrolizumab will be defined as any dose of 1,000 mg or greater (≥ 5 times the indicated dose). No specific information is available on the treatment of pembrolizumab overdose. Appropriate supportive treatment should be provided if clinically indicated. In the event of overdose, the subject should be observed closely for signs of toxicity. Appropriate supportive treatment should be provided if clinically indicated.

If an AE(s) is associated with (“results from”) pembrolizumab overdose, the AE(s) is reported as a SAE, even if no other seriousness criteria are met.

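### Table 6 asks whether the study treatment caused an adverse event, but its later components and its only two recordable answers refer to the Merck product (pembrolizumab), and nothing says which attribution governs

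*Combined protocol and SAP*

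**What the plan says.** Section 7.2 lists what to determine for each adverse event, including "Relationship to the study treatment (Reasonable possibility that AE is related: No, Yes").

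Section 7.2.4, Table 6, then sets out how to judge causality. Its relationship row opens in the same terms: "Did the study treatment cause the AE"? It introduces exposure, time course and likely cause with "The following components are to be used to assess the relationship between the study treatment and the AE".

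The continuation of that row changes the referent: "The following components are to be used to assess the relationship between Merck product and the AE: (continued"). Dechallenge, rechallenge and consistency are worded for the Merck product. The investigator is then told to record one of two answers, "Yes, there is a reasonable possibility of Merck product relationship" or "No, there is not a reasonable possibility of Merck product relationship". Grounds for the second answer include "Subject did not receive the Merck product OR temporal sequence of the AE onset relative to administration of the Merck product is not reasonable", and also that some cause other than the Merck product is the likelier explanation.

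Section 9.1 identifies pembrolizumab as the product that Merck supplies.

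Section 3.2, objective 4, concerns the toxicities of ADV/HSV-tk plus valacyclovir with SBRT given before pembrolizumab. Its definition begins "Toxicity will be defined as any treatment-related death" and adds Grade 3 or higher hematological toxicity. Section 8.1 also lists treatment-related death among the safety summaries.

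**The concern.** Three of the four trial components are not the Merck product, and they are the ones named in the toxicity objective. If the recorded answer concerns pembrolizumab alone, an event caused by the injection, the prodrug or the radiation has no answer on that scale that marks it as related. A death of that kind could then be left out of treatment-related death. A late non-fatal serious event could be judged not reportable. The trial is single-arm, so there is no control group against which to recover a missing attribution. It rests on the investigator's judgment at the time.

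**Working it through.** The plan states no figure on this point, so there is none to reproduce. The check is a comparison of wording plus one day count.

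**1. What each place refers to**

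| Place | Referent |
|---|---|
| Section 7.2, relationship item | Study treatment |
| Table 6, row label and opening question | Study treatment |
| Table 6, exposure, time course, likely cause | Study treatment |
| Table 6, dechallenge and rechallenge | Merck product (the notes also speak of the Sponsor's product) |
| Table 6, consistency | Merck product |
| Table 6, Yes and No answers | Merck product |
| Section 7.2.3.1, any-time SAE duty | Study treatment |
| Sections 3.2(4) and 8.1 | Treatment-related, not defined further |

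**2. Time before any exposure to the Merck product**

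Inputs are from Table 2, Section 5.2.2 and flow-chart footnote l: vector on Day 0, valacyclovir on Days 1–15, radiation on Days 2–16, first pembrolizumab on Day 17 ±1. The flow chart allows ±5 days for visits in general except where otherwise specified, and footnote l specifies ±1 day for this infusion.

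If the first infusion is on Day D, the unexposed days are 0 to D − 1, which is D days.

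- D = 17: Days 0–16, 17 days
- D = 16: Days 0–15, 16 days
- D = 18: Days 0–17, 18 days

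The planned dosing of the other three components falls on Days 0–16.

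**3. The same event on both scales**

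| Event | Table 6 answer, read literally | Section 7.2 answer |
|---|---|---|
| Injection complication on Day 0 | No (Merck product not received) | Yes |
| Radiation-caused event first seen after pembrolizumab has started | No (another cause likelier) | Yes |
| Pembrolizumab-caused event | Yes | Yes |

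The two scales part for the first two rows.

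**4. Which outputs depend on the answer**

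| Output | Depends on attribution? |
|---|---|
| Frequency of all AEs and laboratory abnormalities; worst grade per patient (8.1) | No |
| Grade 3 or higher hematological limb of objective 4 | No attribution wording |
| SAEs to 90 days after treatment, or 30 days if new anticancer therapy starts (7.2.3.1) | No, apart from the exception for progression |
| Deaths more than 30 days after the last pembrolizumab dose (footnote m) | No |
| Treatment-related death (3.2(4), 8.1) | Yes |
| Run-in toxicity count (8.1) | Only through the death limb, and only if the 3.2(4) definition applies; 8.1 does not say |
| SAEs after the fixed period (7.2.3.1) | Yes |

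**The case against.** The best defense is that this is leftover template wording under a question that is plainly about study treatment. The row label, the opening question and the first three components all say so. Table 6 calls its criteria guidance and leaves the answer to the investigator's best clinical judgment. Section 7.2 separately asks for relationship to study treatment, so a vector-caused event can be recorded as related there. A No for the Merck product and a Yes for study treatment answer different questions and can both be true. The CRF is not among the documents, so the field it carries is unknown.

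Most of that stands, and it rules out three stronger readings that a reader might infer.

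- **That Table 6 judges causality solely against pembrolizumab, so such events have to be scored No.** Its opening part uses study treatment, its criteria are guidance, and Section 7.2 permits Yes.
- **That the recorded related rate for the vector, valacyclovir and radiation would be near zero by construction.** The plan defines no such rate. The 17-day window measures exposure and does not count misclassified events.
- **That vector dose de-escalation in Section 5.2.1.2 would fail to trigger.** That section does not refer to Table 6, and an event before the first infusion cannot be due to pembrolizumab.

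The guidance argument does not cure the answer labels. Discretion applies to how the criteria are weighed, but the instruction is to record one of two statements, and both are about the Merck product. An investigator who is sure that the injection caused an event still cannot truthfully choose the Yes statement. The documents do not say that two separate attributions are kept, nor which one defines treatment-related.

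**Conclusion.** The contradiction is real and internal to the protocol: Table 6 disagrees with its own opening question and with Section 7.2. Taken literally, its recording scale gives No for events caused by three of the four components, including any with onset in the 17 days (16–18) before pembrolizumab.

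The consequence is narrow. Adverse events are still collected and tabulated. What is exposed is the classification of treatment-related death, the run-in count if it uses the death limb of objective 4, and the reporting of late related SAEs. For the last of these, the exposure is mainly non-fatal events, because footnote m captures late deaths whatever their cause. No number of affected events can be given.

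The effect arises only if the Table 6 answer is the one carried into the CRF or used to define treatment-related; the documents leave that open. The point is should-fix.

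**What to change.** In Table 6, replace Merck product (and Sponsor's product in the notes) with study treatment in the dechallenge, rechallenge and consistency rows and in the Yes and No answers. For dechallenge and rechallenge this changes little for the vector, since the table already treats both as not applicable to a product used once.

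State that treatment-related in Sections 3.2(4), 7.2.3.1 and 8.1 means a reasonable possibility of relationship to any component: ADV/HSV-tk including the injection procedure, valacyclovir, SBRT/3D RT or pembrolizumab. Say in Section 8.1 whether the run-in uses the 3.2(4) definition.

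Optionally, record Yes or No for each component and keep the pembrolizumab answer for reporting to Merck. No passage promises this, and the contradiction is cured without it, but it would show which component is suspected.

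The cost of the required change is protocol wording, with a matching CRF label if the form follows Table 6. The option adds a few CRF fields per adverse event. Neither adds a procedure for patients. The change is best made before data are collected, because attribution is hard to reconstruct afterwards.
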